5.2. Exclusion Criteria

Any potential participant who meets any of the following criteria will be excluded from participating in the study:

Medical Conditions

1. has a current diagnosis or signs or symptoms of severe, progressive, or uncontrolled renal, cardiac, vascular, pulmonary, gastrointestinal, endocrine, neurologic, hematologic, rheumatologic, psychiatric, or metabolic disturbances.
2. has unstable cardiovascular disease, defined as a recent clinical deterioration (eg, unstable angina, rapid atrial fibrillation) in the last 3 months or a cardiac hospitalization within the last 3 months; has a QT corrected according to Fridericia's formula (QTcF) interval >450 msec for males, and >470 msec for females, has a complete left or right bundle branch block, or has a history or current evidence of additional risk factors for torsades de pointes (eg, heart failure, hypokalemia, family history of Long QT Syndrome) at screening or at Day 1/Week 0 (baseline).
3. Criterion modified per Amendment 1
has a history of lymphoproliferative disease, including lymphoma; a history of monoclonal gammopathy of undetermined significance; or signs and symptoms suggestive of possible lymphoproliferative disease, such as lymphadenopathy or splenomegaly.
4. a history of malignancy within 5 years before screening (exceptions are squamous and basal cell carcinomas of the skin and carcinoma in situ of the cervix, or malignancy, which is

considered cured with no evidence of recurrence for at least 3 months prior to the first administration of study intervention and with minimal risk of recurrence).

5. has a history of chronic or recurrent infectious disease, including but not limited to chronic renal infection, chronic chest infection (eg, bronchiectasis), recurrent urinary tract infection (recurrent pyelonephritis or chronic nonremitting cystitis), fungal infection (mucocutaneous candidiasis), or open, draining, or infected skin wounds or ulcers.
6. has or has had a serious infection (eg, sepsis, pneumonia, or pyelonephritis), or has been hospitalized or received IV antibiotics for an infection during the 2 months before screening.
7. has or has had herpes zoster within the 2 months before screening.
8. has a history of an infected joint prosthesis or has received antibiotics for a suspected infection of a joint prosthesis, if that prosthesis has not been removed or replaced.
9. has a history of being human immunodeficiency virus (HIV) antibody-positive, or tests positive for HIV at screening.
10. Criterion modified per Amendment 1

tests positive for hepatitis B virus (HBV) infection (see Section 10.8, Appendix 8: HBV Screening with HBV DNA Testing) or has clinically active liver disease, or is seropositive for antibodies to hepatitis C virus (HCV) at screening unless they satisfy one of the following conditions:

- have a history of successful treatment (defined as being negative for HCV ribonucleic acid [RNA] at least 6 months after completing antiviral treatment) and have a negative HCV RNA test result at screening,

OR

- while seropositive, have a negative HCV RNA test results at least 6 months prior to screening and a negative HCV RNA test result at screening regardless of vaccination status.

11. During the 6 weeks prior to baseline, have had any of (a) confirmed severe acute respiratory syndrome coronavirus 2 (SARS-CoV-2; Coronavirus Disease 2019 [COVID-19]) infection (test positive), OR (b) suspected serious adverse reactions (SARs)-CoV-2 infection (clinical features without documented test results), OR (c) close contact with a person with known or suspected SARS-CoV-2 infection.

An exception to this criterion maybe granted if a participant has a documented negative result for a validated SARS-CoV-2 test:

- a. Obtained at least 2 weeks after conditions (a), (b), (c) above (timed from resolution of key clinical features if present, eg, fever, cough, dyspnea)

AND

- b. with absence of ALL conditions (a), (b), (c) above during the period between the negative test result and the baseline study visit.

NOTES on COVID-19-related exclusion:

- a. The field of COVID-19-related testing (for presence of, and immunity to, the SARS CoV-2 virus) is rapidly evolving. Additional testing may be performed as part of screening and/or during the study if deemed necessary by the investigator and in accordance with current regulations / guidance from authorities / standards of care.
- b. Precaution: for those who may carry a higher risk for severe COVID-19 illness, follow guidance from local health authorities when weighing the potential benefits and risks of enrolling in the study, and during participation in the study.

12. Criterion modified per Amendment 1

has a history of latent or active granulomatous infection, including histoplasmosis or coccidioidomycosis, prior to screening. Participants with radiographic evidence of possible prior histoplasmosis or coccidioidomycosis will be excluded. Refer to Inclusion Criterion 20 for information regarding eligibility with a history of latent TB.

13. has a chest radiograph within 3 months before the first administration of study intervention that shows an abnormality suggestive of a malignancy or current active infection, including TB. A chest CT scan is also acceptable if already available or obtained outside of the study protocol.
14. has ever had a nontuberculous mycobacterial infection or opportunistic infection (eg, cytomegalovirus, pneumocystis, aspergillosis).
15. has 2 indeterminate (on repeat sampling) QuantiFERON®-TB test results.
16. has had major surgery (eg, requiring general anesthesia and hospitalization) within 8 weeks before screening, or has not fully recovered from such surgery, or has such surgery planned during the time the participant is expected to participate in the study.
17. has a transplanted organ (with exception of a corneal transplant >3 months before the first administration of study intervention).
18. known allergies, hypersensitivity, or intolerance to bermekimab or its excipients (refer to the [IB](#)).

Prior/Concomitant Therapy

19. has taken any of the medications or therapies outlined in the inclusion/exclusion criteria within the specified period, or has plans to receive any disallowed therapies as noted in Section [6.8](#), Concomitant Therapy throughout the study.
20. has ever received any IL-1 antagonist (eg, including but not limited to anakinra, rilonacept)
21. has previously received dupilumab.
22. has received an immunomodulating biologic therapy within the previous 3 months of study intervention administration (including, but not limited to, anti-cytokine, anti-complement antibodies, anti-Ig antibodies, etc).
23. has received phototherapy or any systemic medications/treatments that could affect AD or IGA evaluations within 4 weeks of the first administration of any study intervention.
24. Criterion modified per Amendment 1

use of any prescription topical treatment for AD within 4 weeks of the baseline visit, including prescription moisturizer, unless the prescribed moisturizer can be obtained over the counter (OTC) and it doesn't require a prescription.

25. Criterion modified per Amendment 1

has received systemic immunosuppressant, immunomodulatory, or cytotoxic treatments (including, but not limited to, oral or injectable corticosteroids, cyclosporin, or methotrexate) that could affect AD or IGA evaluations within 4 weeks before the baseline visit, or any condition other than AD that, in the opinion of the investigator, is likely to require such treatment(s) within 4 weeks before the baseline visit.

26. has received natalizumab, belimumab, or agents that modulate B cells or T cells (eg, rituximab, alemtuzumab, abatacept, or visilizumab) within 12 months of the first administration of study intervention.

27. has received, or is expected to receive, any live virus or bacterial vaccination within 12 weeks before the first administration of study intervention. Non-live vaccines approved or authorized for emergency use (eg, COVID-19) by local health authorities are allowed.

28. has had a Bacille Calmette-Guerin (BCG) vaccination within 12 months prior to screening.

Prior/Concurrent Clinical Study Experience

29. has received any non-biologic investigational intervention (including investigational vaccines) within 30 days or 5 half-lives (whichever is longer) of any study intervention administration or is currently enrolled in another study using an investigational agent, device, or procedure

30. has known intolerance or hypersensitivity to any biologic medication, or known allergies or clinically significant reactions to murine, chimeric, or human proteins, mAbs, or antibody fragments.

31. is pregnant, or breast-feeding, or planning to become pregnant while enrolled in this study or within 12 weeks after the last dose of study intervention.

32. plans to father a child while enrolled in this study or within 12 weeks after the last dose of study intervention.

33. any condition for which, in the opinion of the investigator, participation would not be in the best interest of the participant (eg, compromise the well-being) or that could prevent, limit, or confound the protocol-specified assessments.

Diagnostic Assessments – Not applicable

Other Exclusions

34. employee of the investigator or study site, with direct involvement in the proposed study or other studies under the direction of that investigator or study site, as well as family members of the employees or the investigator

35. Criterion modified per Amendment 1

history of drug or alcohol abuse according to Diagnostic and Statistical Manual of Mental Disorders (5th edition) criteria within 12 months before screening.

Note: Investigators should ensure that all study enrollment criteria have been met at screening. If a participant's clinical status changes (including any available laboratory results or receipt of additional medical records) after screening but before the first dose of study intervention is given such that he or she no longer meets all eligibility criteria, then the participant should be excluded from participation in the study. Section 5.4, Screen Failures, describes options for retesting. The required source documentation to support meeting the enrollment criteria are noted in Section 10.3, Appendix 3, Regulatory, Ethical, and Study Oversight Considerations.

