5. STUDY POPULATION

Screening for eligible participants will be performed within 4 weeks before administration of the study intervention. Refer to Section 5.4, Screen Failures for conditions under which the repeat of any screening procedures is allowed.

The inclusion and exclusion criteria for enrolling participants in this study are described below. If there is a question about these criteria, the investigator must consult with the appropriate sponsor representative and resolve any issues before enrolling a participant in the study. Waivers are not allowed.

For a discussion of the statistical considerations of participant selection, refer to Section 9.1, Sample Size Determination.

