 - Within 2 months before the first administration of study intervention, have a negative QuantiFERON-TB test result, or have a newly identified positive QuantiFERON-TB test result (see laboratory manual) in which active TB has been ruled out and for which appropriate treatment for latent TB has been initiated before the first administration of study intervention. Within 2 months before the first administration of study intervention, a negative tuberculin skin test, or a newly identified positive tuberculin skin test in which active TB has been ruled out and for which appropriate treatment for latent TB has been initiated before the first administration of study intervention, is additionally required if the QuantiFERON-TB test is not approved/registered in that country or the tuberculin skin test is mandated by local health authorities.

NOTE A negative tuberculin skin test result (see Section 10.6, Appendix 6: Tuberculin Testing) is additionally required if the QuantiFERON-TB test is not approved/registered in the country in which this protocol is being conducted. In Ukraine, while the QuantiFERON TB test is not approved/registered, it is acceptable, and an additional tuberculin skin test is not required. The QuantiFERON-TB test and the tuberculin skin test are not required at screening for participants with a history of latent TB, if active TB has been ruled out, and if appropriate treatment has been initiated/completed as described above in Inclusion Criterion 20a.

- a. Have a chest radiograph (both posterior-anterior and lateral views, or per country regulations where applicable), taken within 12 weeks before the first administration of study intervention and read by a radiologist or qualified pulmonologist, with no evidence of current, active TB or old, inactive TB. A chest computed tomography (CT) scan is also acceptable if already available or obtained outside of the study protocol.

Miscellaneous

20. must be willing and able to complete electronic patient reported outcome (ePRO) questionnaires and diaries (Section 8.1, Efficacy Assessments) per the Schedule of Activities (SoA; Section 1.3).
21. willing and able to adhere to the lifestyle restrictions specified in this protocol.
22. must be willing to undergo 4 skin biopsies.

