A participant whose first QuantiFERON-TB test result is indeterminate should have the test repeated. In the event that the second QuantiFERON-TB test result is also indeterminate, the participant may be enrolled without treatment for latent TB if active TB is ruled out, their chest radiograph shows no abnormality suggestive of TB (active or old, inactive TB) and the participant has no additional risk factors for TB as determined by the investigator. For sites in Japan, a participant whose first T-SPOT test result is borderline should have the test repeated. In the event that the second T-SPOT (for sites in Japan) test result is also borderline, the participant may be enrolled without treatment for latent TB if active TB is ruled out, their chest radiograph shows no abnormality suggestive of TB (active or old, inactive TB) and the participant has no additional risk factors for TB as determined by the investigator. This determination must be promptly reported to the medical monitor or designee and recorded in the participant's source documents and initialed by the investigator.

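### Section 8.2.9.1 lets a site enrol some people with two indeterminate QuantiFERON-TB results whom the eligibility criteria in Section 5 exclude

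*Protocol*

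**What the plan says.** **Eligibility (Protocol Section 5).** The exclusion list opens with "Any potential participant who meets any of the following criteria will be excluded from participating in the study". Criterion 15 on that list covers a person who "has 2 indeterminate (on repeat sampling") QuantiFERON-TB results. It carries no exception and no cross-reference to the TB procedures.

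Section 5.1 requires every inclusion criterion to be met. On the TB test, criterion 19 requires a person to "have a negative QuantiFERON-TB test result, or have a newly identified positive QuantiFERON-TB test result"; the positive branch also requires that active TB has been excluded and latent-TB treatment started. A note exempts people with a history of latent TB from testing if active TB is excluded and treatment has been started or completed as the criterion describes.

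For questions about the criteria, Section 5 says "the investigator must consult with the appropriate sponsor representative and resolve any issues before enrolling a participant in the study. Waivers are not allowed". The note closing Section 5.2 adds: "Investigators should ensure that all study enrollment criteria have been met at screening".

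**TB procedures (Protocol Section 8.2.9.1).** After one indeterminate result the test is repeated. Then: "In the event that the second QuantiFERON-TB test result is also indeterminate, the participant may be enrolled without treatment for latent TB", subject to three conditions: active TB excluded, no radiographic sign of active or old TB, and no further TB risk factor in the investigator's judgement. A matching sentence for sites in Japan says that if "the second T-SPOT (for sites in Japan) test result is also borderline, the participant may be enrolled without treatment for latent TB", on the same conditions. The paragraph ends with a reporting duty: "This determination must be promptly reported to the medical monitor or designee", together with an entry in the source documents.

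**The concern.** The two sections address the same event, a repeated test that is again indeterminate, and give different answers for some of the people concerned. Section 8.2.9.1 is not background procedure: it states who is eligible to continue towards randomization and who can be enrolled. A site working from it could reasonably believe that it was following the protocol.

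The stakes are safety and consistency. Table 1 in Section 2.3.1 lists infection first among the risks of bermekimab and relies on excluding people with active or untreated latent infection, including TB. The permission admits people whose latent-TB status has not been settled, and without treatment. Sites could also decide identical cases differently. A site using the permission could be recorded under the SAP's major-deviation category for people who entered without meeting the criteria (SAP Appendix 4).

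**Working it through.** No arithmetic applies. The check takes one person through each rule: two indeterminate QuantiFERON-TB results at screening, active TB excluded, a clear chest radiograph, no added risk factors, and no history of latent TB.

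| Place in the protocol | Force | Result for this person |
|---|---|---|
| 5.2, exclusion 15 | Mandatory; one criterion suffices | Excluded |
| 5.1, inclusion 19 | Mandatory; all criteria required | Not met: the result is neither negative nor newly positive with treatment started |
| 8.2.9.1 | Permissive | Enrolment allowed without latent-TB treatment |

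1. **Could exclusion 15 contain an implied exception?** The wording does not suggest one. Exclusions 4, 10, 11 and 17 in the same list write their exceptions out; criterion 15 has none.

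2. **Is inclusion 19 merely silent?** No. It requires one of two test outcomes, and a person with two indeterminate results has neither. Outside the exemption for prior latent TB, it is a second bar. The tally is therefore two mandatory criteria against one permission.

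3. **Does Section 5 settle the matter?** It points clearly to exclusion: the list is mandatory, all inclusion criteria must be met, and waivers are ruled out. No clause, however, tells the reader of 8.2.9.1 that Section 5 overrides it. The permission is a standing rule rather than a waiver granted case by case, so the no-waiver sentence need not alert a site using it.

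4. **Does the medical-monitor report act as a gate?** The text asks for prompt reporting. It does not say that the report precedes enrolment or that agreement is needed.

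5. **Does Section 7.1 add to the conflict?** It stops study intervention when a participant under evaluation has two indeterminate results, so it treats that result as disqualifying. But it governs continued dosing rather than enrolment, and it is not counted here.

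6. **Who is affected?** Only people who meet all three conditions in 8.2.9.1. Anyone else with two indeterminate results is barred under both sections.

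Both rules are current protocol text. The mismatch does not come from redaction, text extraction or the amendment summary.

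**The case against.** The strongest reply is that there is no real contradiction. Section 5 commands and 8.2.9.1 only permits, so a site that excludes the person breaches nothing. Section 5 also requires questions about the criteria to be resolved with the sponsor before enrolment. That control comes before dosing and is stronger than the report in 8.2.9.1. Eligibility is reviewed at screening and Week 0, and TB evaluation recurs through the study.

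Much of this stands. A reader might infer that the protocol leaves it open which section governs. The documents do not support that: read together, the provisions of Section 5 make this person ineligible. What remains is that the permission is wrong as written. The consultation duty depends on the site seeing a question, and a site that finds an express permission may see none.

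A reader might also infer that a second borderline T-SPOT result should be added to criterion 15. That is not supported either. No exclusion criterion contradicts the T-SPOT permission, footnote i to the Schedule of Activities says that all participants have QuantiFERON-TB testing, and the documents do not confirm any site in Japan. Adding it would create a new exclusion while leaving inclusion 19 with no T-SPOT route at all, even for a negative result.

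**Conclusion.** The point holds as a small eligibility and safety inconsistency. Exclusion 15 and inclusion 19 both keep out a person with two indeterminate QuantiFERON-TB results, subject to the prior-latent-TB exemption in the latter. Section 8.2.9.1 would lead a site to enrol and dose some of those people.

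Its reach is narrow. The documents give no frequency for a second indeterminate result, and nothing in them shows that the permission was used. There is no effect on power, the type I error rate or the primary analysis. The SAP records early termination with few participants and listings only, so the practical effect in this trial is small. The correction would matter most if the TB text were reused in another protocol.

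The conclusion rests on taking Section 5 at its plain wording and on the absence of an overriding instruction in the two documents. Training material or site instructions outside them could have given sites one answer.

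**What to change.** In Section 8.2.9.1, delete the permission to enrol after a second indeterminate QuantiFERON-TB result and state that such a result means exclusion under criterion 15. This matches both mandatory criteria and needs no change to Section 5.

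If the sponsor intended the permission, write it as an explicit exception into both exclusion 15 and inclusion 19, with the three conditions and a report to the medical monitor before enrolment.

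Leave T-SPOT out of criterion 15. If sites in Japan will use that test, align inclusion 19 and 8.2.9.1 for it as a separate change.

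The cost is wording in an amendment. Deleting the permission may add a few screen failures.

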5.3. Lifestyle Considerations

Potential participants must be willing and able to adhere to the following lifestyle restrictions during the course of the study to be eligible for participation:

1. A woman of childbearing potential who is heterosexually active must remain on a highly effective method of birth control (inclusion criterion 10) during the study and for at least 12 weeks after receiving the last administration of study intervention.
2. A woman must agree not to donate eggs (ova, oocytes) during the study and for a period of at least 12 weeks following the last administration of study intervention.
3. A man who is sexually active with a female of childbearing potential and has not had a vasectomy must agree to use a barrier method of birth control (See inclusion criterion 12) during the study and for at least 12 weeks after receiving the last administration of study intervention.
4. A man must agree to not donate sperm during the study and for at least 12 weeks after receiving the last administration of study intervention.
5. Participants must comply with restrictions on concomitant medications and therapies specified in the protocol (refer to Section 6.8, Concomitant Therapy, for details).
6. All participants are required to apply moisturizers at least once daily for at least 7 days before randomization and continue the treatment throughout the study (including the safety follow-up period; see Section 6.8, Concomitant Therapy, for details).
7. Participants must not receive a live virus or bacterial vaccination during the study and for 3 months after the last administration of any study intervention. See lifestyle consideration for information regarding BCG vaccination.
8. Participants must not receive a BCG vaccination during the study and for 12 months after the last administration of any study intervention.
9. Agree to follow all requirements that must be met during the study as noted in the inclusion and exclusion criteria (eg, contraceptive requirements).
10. Criterion modified per Amendment 1

It is strongly recommended that participants are up-to-date on age-appropriate vaccinations including COVID-19 vaccines prior to screening as per routine local medical guidelines. For study participants who received locally-approved (and including emergency use-authorized) COVID-19 vaccines recently prior to study entry, follow applicable local vaccine labelling,

guidelines, and standards of care for patients receiving immune-targeted therapy when determining an appropriate interval between vaccination and study enrolment (see also Section [6.8](#) Concomitant Therapy).

